1. BACKGROUND AND RATIONALE

Vaccination is considered the best approach to lower the burden of influenza disease. The efficacy in older individuals is significantly lower due to the aging of the immune system (i.e. immunosenescence) and underlying medical conditions that can both increase the risk of influenza complications as well as interfere with immune responses ([Sasaki et al. 2011](#)).

One way to increase the immunogenicity of influenza vaccines is by using adjuvants, such as the squalene and water emulsion adjuvant, MF59.

Although the current licensure of Fluad (trivalent and quadrivalent) is limited to persons 65 years of age and older, the results of clinical studies conducted in healthy individuals 50-64 years and subjects 18-60 years of age with chronic medical conditions, demonstrated similar benefits as has been seen in adults 65 years of age and older in terms of immunogenicity ([O'Hagan et al. 2011](#); [Noh et al. 2016](#); [Baldo et al. 2007](#)). Like the findings with older adults an acceptable safety and tolerability profile was seen in adults under 65 years of age.

Apart from the medical need for improved vaccines in people aged 50 to 65 years, determining persistence beyond a typical seasonal epidemic is important, considering that influenza persists in the temperate climate zone for more than 6 months. Persistence of vaccine-induced immunity over periods longer than a typical winter season has not been widely investigated.

The purpose of this study is to demonstrate that vaccination with MF59-adjuvated Quadrivalent Influenza Vaccine (aQIV) elicits an immune response that is non-inferior to Quadrivalent Influenza Vaccine (QIV) with respect to the Geometric Mean Titer ratio (GMTr) and Seroconversion Rate (SCR) difference for each vaccine strain contained within the vaccine. Furthermore, if the non-inferiority comparisons are successful, the study is designed to assess superior immune response with regards to GMTr of aQIV compared with a licensed non-adjuvanted quadrivalent influenza vaccine for two out of four vaccine strains, three weeks after vaccination in adults 50-64 years of age. In addition, antibody persistence, reactogenicity and safety will be assessed. Data from this study will be used to expand the licensure of the quadrivalent version of Fluad for the prevention of seasonal influenza in adults 50-64 years of age.

For further details of the background of the study, please refer to section 1.0 of the protocol.

This Statistical Analysis Plan (SAP) describes the data and variables to be summarized and analyzed, including specifics of the statistical analyses to be performed and is based on protocol version 3.0 dated 11JUL2022. It is compliant with International Conference on Harmonization (ICH) Harmonized Tripartite Guideline, 5 February 1998, Statistical Principles for Clinical Trials, E9; World Health Organization, WHO Technical Report, Series No. 924. 2004, Annex 1: Guidelines on Clinical Evaluation of Vaccines: Regulatory Expectations; and FDA Center for Biologics Evaluation and Research (CBER) Guidance for Industry, May 2007, Clinical Data Needed to Support the Licensure of Seasonal Inactivated Influenza Vaccines.

2. OBJECTIVES

2.1 Primary Objectives

2.1.1 Primary Immunogenicity Objective

- 1a. To demonstrate immunological non-inferiority of aQIV versus a non-adjuvanted quadrivalent influenza vaccine comparator (QIV) in subjects 50-64 years of age, as measured by hemagglutination inhibition (HI)¹ geometric mean titers (GMTs) and seroconversion rates (SCRs) for each vaccine strain, at 3 weeks after vaccination.

Success criteria:

Non-inferiority will be demonstrated if the UL of the two-sided 95% confidence interval (CI) for inter-group GMT ratio² (QIV/aQIV) is ≤ 1.5 for each vaccine strain, and the upper limit (UL) of the two-sided 95% CI around the difference in SCR³ (QIV-aQIV) is $\leq 10\%$ for each vaccine strain.

- 1b. To demonstrate that aQIV induces a superior immune response compared with QIV in subjects 50-64 years of age as measured by HI¹ GMTs at 3 weeks after vaccination for at least 2 of the 4 vaccine strains.

Success criteria (after objective 1a is reached):

Superior immune response will be demonstrated if the UL of the two-sided 95% CI for inter-group GMT ratio (QIV/aQIV) < 1.0 for at least 2 of the 4 vaccine strains

2.2 Secondary Objectives

2.2.1 Secondary Immunogenicity Objective(s)

- 2a. To demonstrate that aQIV induces a superior immune response compared with QIV in subjects 50-64 years of age as measured by HI GMT for at least one vaccine strain at 3 weeks after vaccination.

¹ In case of lack of agglutination or agglutination mediated through neuraminidase for a specific strain using HI assay, immunogenicity for that strain will be assessed as measured by microneutralization (MN) assay as an acceptable alternative.

² The GMT ratio is defined as the geometric mean of the post-vaccination HI titer for QIV over the geometric mean of postvaccination HI titer for aQIV.

³ The SCR is defined as the percentage of subjects with either a pre-vaccination HI titer $< 1:10$ and a post-vaccination HI titer $\geq 1:40$ or a pre-vaccination HI titer $\geq 1:10$ and a ≥ 4 -fold increase in postvaccination HI titer. Difference in SCR is defined as $SCR_{QIV} - SCR_{aQIV}$.

Statistical Analysis Plan, Protocol Number V118_23
20OCT2022 Final Version 1.0

Success criteria:

Superior immune response will be demonstrated if the UL of the two-sided 98.73% CI for inter-group GMT ratio (QIV/aQIV) < 0.67 for one or more vaccine strains.

- 2b. To demonstrate greater persistence of the immune response for at least one vaccine strain at 6 months after vaccination with aQIV compared with QIV as measured by HI in subjects 50-64 years of age.

Success criteria:

Greater persistence of the immune response will be demonstrated if the UL of the two-sided 98.73% CI for inter-group GMT ratio (QIV/aQIV) < 1.0 for one or more vaccine strains.

- 2c To evaluate the immunogenicity of aQIV compared with QIV as measured by HI in subjects 50-64 years of age.

2.2.2 Secondary Safety Objective:

To assess the safety and reactogenicity of aQIV and QIV in adults 50-64 years.

2.3 Exploratory Objectives

To evaluate persistence of the immune response at 9 months after vaccination with aQIV compared with QIV as measured by HI in subjects 50-64 years of age.

To further evaluate the immunogenicity of aQIV compared with QIV in subjects 50-64 years of age, with alternative assays, if sera permit.

3. STUDY DESIGN

Experimental design: This is a Phase 3, randomized, comparator controlled, observer-blind, multi-center study in approximately 2,018 adults 50-64 years of age.

Duration of the study: The study duration is approximately 9 months for each subject.

Vaccination schedule: single vaccination (Day 1).

Study vaccine: aQIV vaccine (Fluad Tetra/Quadrivalent).

Comparator vaccines: non-adjuvanted QIV (██████████).

Treatment groups:

aQIV group: approximately 1,009 subjects receiving one dose of aQIV at Day 1.

QIV group: approximately 1,009 subjects receiving one dose of QIV at Day 1.

Randomization: An Interactive Response Technology (IRT) system will be used in the study. Subjects will be enrolled and stratified equally into two age groups (50-59 years and 60-64 years) with approximately 50% of subjects per age group. Within each age group subjects will be randomized to the aQIV or QIV according to a 1:1 ratio. Stratification for history of any influenza vaccination within 3 previous seasons (yes/no) will be applied to all subjects.

Blinding: Observer-blind study.

Blood sample schedule: Four blood samples (approximately 10 mL each)⁴ will be collected from all subjects on Days 1, 22, 181 and 271.

Data collection: electronic Diary (eDiary), electronic Case Reporting Form (eCRF).

Study clinic visits: Four clinic visits for each subject at Days 1, 22, 181 and 271.

Safety phone call: Two safety phone calls (Day 15 and Day 91) will be conducted: on Day 15 to collect any unsolicited adverse events (AEs), including associated medications and any vaccinations, on Day 91 to collect only serious AEs (SAEs), AEs leading to withdrawal, AEs

⁴ Subjects may be asked to voluntarily provide extra blood samples of 50 mL at Day 1 and Day 22, that can be used for future research not directly related to this study, but with the purpose to improve the understanding of the influenza vaccines or disease.

Statistical Analysis Plan, Protocol Number V118_23
20OCT2022 Final Version 1.0

of special interest (AESIs), and concomitant medications associated with these events and any vaccinations.

Solicited AEs occurring on the day of study vaccination through the following 6 days (Day 1 through Day 7, or longer if the events are not resolved), will be recorded daily using an eDiary as completed by the subject.

Safety data collection: During the treatment period (Days 1-22) all unsolicited AEs occurring within 21 days (Day 22) after study vaccination will be collected. During the follow-up period (Days 23-271) only SAEs, AEs leading to study withdrawal, and AESIs will be collected. These data will be captured by interviewing the subject during the clinic visits, during the safety phone calls scheduled to occur on Days 15 and 91 and by review of available medical records. Subjects will be instructed to call the site in the event of any AE which they perceive as being of concern during the entire study period.

Serological assays:

HI assay for homologous vaccine strains, using egg-derived target virus, will be performed for all subjects on serum samples collected on Days 1, 22, 181 and 271.

Written informed consent will be obtained before conducting any study-specific procedures.

Table 1 Time and Events Schedule

Study Event	References**	Visit Type	Clinic Visit	Safety Phone Call	Clinic Visit*	Safety Phone Call	Clinic Visit*	Clinic Visit*
Study Day		1	15	22	91	181		271
Visit Window (Days)		n/a	-3/+3	-3 to +7	-7 to +7	-14 to +14		-14 to +14
Visit Number		1	2	3	4	5		6
Study Treatment								
Vaccination	Section 5.2		X					
Screening and Safety								
Informed Consent ^a	Section 5.1.1		X					
Demographics and baseline characteristics	Section 5.1.2		X					
Medical History ^b	Section 5.1.2		X					
Physical Exam ^c	Section 5.1.2		X		X		X	
Pregnancy Test ^d	Section 5.1.2		X					
Exclusion/Inclusion Criteria	Section 4		X					
Randomization	Section 5.1.4		X					

Visit Type	Clinic Visit	Safety Phone Call	Clinic Visit*	Safety Phone Call	Clinic Visit*	Clinic Visit*
Study Day	1	15	22	91	181	271
Visit Window (Days)	n/a	-3/+3	-3 to +7	-7 to +7	-14 to +14	-14 to +14
Visit Number	1	2	3	4	5	6
Study Event	References**					
30 Minutes Post Injection Assessment of unsolicited AEs	Section 5.3	X				
Subject eDiary Dispensed with Training	Section 5.3	X				
Review of eDiary data and compliance	Section 3.6.2	Ongoing during eDiary use				
Assess all AEs	Section 7.1.2	X	X	X		
Assess SAEs	Section 7.1.4	X	X	X	X	X
Asses for AEs leading to withdrawal, and AESIs	Section 7.1.4.1	X	X	X	X	X
Assess relevant medications and vaccinations	Section 6.5	X	X	X	X	X
Immunogenicity						
Serology blood draw ^e	Section 5.1.5	X ^f			X	X
Study Completion Procedure						

Visit Type	Clinic Visit	Safety Phone Call	Clinic Visit*	Safety Phone Call	Clinic Visit*	Clinic Visit*
Study Day	1	15	22	91	181	271
Visit Window (Days)	n/a	-3/+3	-3 to +7	-7 to +7	-14 to +14	-14 to +14
Visit Number	1	2	3	4	5	6
Study Event	References**					
Study Completion/early termination ^g	Section 5.6					X

Notes: * In the exceptional case that a clinic visit is not possible, and if in line with country and site regulations with appropriate sponsor approvals a home visit may be considered.

** All sections refer to sections of the protocol.

^a Consent form should be signed prior to performing any study procedures. The informed consent process may be conducted earlier, but within 10 days prior to Day 1;

^b Medical history includes existing comorbidities

^c A physical examination will be based on a review of systems, i.e., a structured interview for complaints for each organ system;

^d A pregnancy test should be done for females of childbearing potential;

^e Subjects may be asked to voluntarily provide extra blood samples of 50 mL at Day 1 and Day 22 (see section 3.7 of the protocol, Collection of Clinical Specimens)

^f Blood sample for serology to be taken after temperature measurement, but prior to vaccination;

^g Subjects who terminate the study early will be requested to complete all safety-related Study Completion procedures.

4. RANDOMIZATION AND BLINDING

4.1 Method of Group Assignment and Randomization

Enrolled subjects will be assigned a subject ID and randomized in the IRT system in a 1:1 ratio to receive either aQIV or QIV with age group (50 to 59, and 60 to 64 years of age), and history of any influenza vaccination within 3 previous influenza seasons (yes/no) as stratification factors. Approximately 50% of subjects will be enrolled into each age group. The Subject ID will be the subject's unique identification number for all eCRFs and associated study documentation that will be used for duration of the study. After randomization, the Screening Number ceases to be used and remains in the Screening and Enrolment Log only. The list of randomization assignments is produced by the IRT service provider and approved by Seqirus according to applicable Seqirus Standard Operating Procedure (SOP).

If for any reason, after signing the informed consent form (ICF), the subject who is eligible and enrolled fails to be randomized, this is called a randomization failure and the early termination study procedures must be applied. The reason for all randomization failures should be recorded in the Screening and Enrolment Log and in the source document. The information on subjects who are randomization failures should be kept distinct from subjects who are screen failures, as described in protocol section 5.1.2, Screening.

If for any reason, after randomization the subject fails to undergo treatment or the subject has discontinued, the reason should be recorded in source document and in the eCRF. The information on discontinued subjects should be kept distinct in the source documentation from randomization failures.

4.1.1 Definition of Randomization/Vaccination Errors

The list below provides categories for errors that may occur during randomization and/or vaccination.

Randomization errors:

- Administered wrong kit (Subject received vaccine from a kit different from the kit number that was assigned at randomization).

Vaccination errors:

- Administered only part of the study vaccine.
- Incorrect vaccine administration (e.g. incorrect location or route)
- Administered expired vaccine.
- Administered temperature deviated vaccine.

Stratification error:

- Subject randomized in the wrong stratification stratum.

Differentiate between incorrect stratification and randomization errors.

A randomization error is defined as a subject receiving a vaccine from another kit than the one assigned by randomization. If after unblinding, it appears that the vaccine from the incorrect kit is identical to the vaccine from the assigned kit, the error will be reported as a major protocol deviation (PD), but the data from the subject will not be excluded from any analyses sets. If the vaccine is different from the vaccine in the assigned kit, the randomization error is a Clinical Study Report (CSR) - reportable PD and the subject's data should be analyzed as randomized in Full Analysis Set (FAS), excluded from Per Protocol Set (PPS) and analyzed as received for Safety.

Incorrect stratification is defined as enrollment and randomization of a subject based on incorrect stratification information at baseline. Incorrect stratifications should be split for major and minor errors.

- Major stratification errors are those resulting in administration of incorrect dosage or schedule, not corrected on time, i.e. not corrected before administration of the vaccine. These will be handled as CSR-reportable PD.
- Minor stratification errors are those not having impact on dose/schedule administered. These will not be considered as CSR reportable PD.

Since the vaccine dosage and regimen in this study are independent from the stratification factors, major stratification errors are not applicable. In the analysis of covariance (ANCOVA) and in the subgroup analyses, subjects will be analyzed according to their actual age and/or influenza vaccination history.

Stratification error	FAS	PPS	Safety Sets All-Enrolled Set All-Exposed Set
Minor	Analyze as corrected	Analyze as corrected	Analyze as corrected
Major*	Analyze as originally stratified	Exclude from analysis	Analyze as corrected

* Since the vaccine dosage and regimen in study V118_23 are independent from the stratification factors, major stratification errors are not applicable.

4.1.2 Forced Randomization

Forced randomization will not be utilized in this trial.

4.2 Blinding and Unblinding

The study is designed as an observer-blind study. During the treatment period of the study designated and trained unblinded nurse(s), physician(s), or other qualified health care professional will be responsible for preparing and administering the study vaccines to the subjects. They will be instructed not to reveal the identity of the study vaccines to the subject or to the investigative site personnel (i.e., blinded investigator and study nurse) involved in the monitoring of conduct of the trial, except in an emergency if unblinding in IRT is not possible. Vaccine administration should be shielded from the subject and blinded study personnel. The unblinded personnel should not be involved in data collection or data review such as safety assessments and/or collect study data after the vaccinations. Study vaccines will be assigned through an IRT system.

Except in the case of medical necessity, a subject's treatment should not be unblinded without the approval of the Sponsor. In such instance, every effort should be made to contact the Sponsor prior to unblinding. If unblinding occurs, by either accidental unblinding or emergency unblinding for a SAE, prior to completion of the study, the investigator must promptly contact the Sponsor and document the circumstances in IRT. In case of an emergency, the information can be retrieved by the investigator from the IRT system either via web or phone (a 24/7 backup service).

All personnel involved in the conduct of the study or in the analysis of the final study results, or who have contact with study centers, will remain blinded to the treatment codes until the clinical database has been locked, protocol deviations (except for Day 271 serum sample analysis PDs) have been assessed, and the data have been released for statistical analysis. The analysis on the primary and secondary objectives for the final CSR will be conducted on this data.

All personnel involved in processing samples and performing laboratory assays will remain blinded to the treatment codes until all Day 271 serum samples have been tested and results have been transferred. The exploratory analysis on the 9 month persistence objective will be conducted on this data and reported in a CSR addendum.

If a subject is unblinded during the study, it is to be documented as a CSR-reportable PD. The unblinding will be documented appropriately. The unblinded subject(s) may be excluded from the PPS. Unblinded subjects will be included in the FAS and safety sets. Data from subjects who are unblinded by Pharmacovigilance due to suspected unexpected serious adverse reactions (SUSAR) do not need to be excluded from any analysis set or reported as CSR reportable PD, as long as the clinical study team involved in the data review and analysis remains blinded.

5. SAMPLE SIZE AND POWER CONSIDERATIONS

aQIV will be tested against QIV. The randomization ratio is 1:1 (aQIV:QIV). The study is designed to have at least 90% power to achieve the primary objectives: to demonstrate the noninferiority of GMT and SCR of aQIV vs QIV for all four vaccine strains, and the superiority assessment (superiority margin of 1) of GMT of aQIV vs QIV for at least two out of the four vaccine strains with one-sided significance level $\alpha=0.025$.

The results of a previous clinical study with aTIV and TIV vaccine in subjects 50-64 years of age (V7P38) was used to generate assumptions for the vaccine effects and sample size.

It is assumed that the differences (aQIV minus QIV) of $\log_{10}(\text{GMT})$ of A/H1N1 is 0.07, with standard deviation of 0.46 for both treatment arms, 1,816 evaluable subjects will provide at least 90% of power to demonstrate a superiority (GMTr margin of 1) of aQIV vs QIV for the A/H1N1 strain. The table below shows the power of each comparison based on GMT ratio and SCR data from study V7P38:

Table 2 Sample size and power estimates based on the GMT ratio endpoint

Strain	Log10(GMT) Differences (SD)	Sample Size* (Evaluable) for 90% Power	Power with Sample size of 2,018 for superiority (GMTr margin of 1) (1816 evaluable)	Power with Sample size of 2,018 for NI (GMTr Margin of 0.67)
A/H1N1	0.07 (0.46)	2,018 (1,816 evaluable)	90%	~100%
A/H3N2	0.26 (0.61)	260 (234 evaluable)	~100%	~100%
B (Victoria and Yamagata lineage)	0.14 (0.48)	552 (496 evaluable)	~100%	~100%

*Based on 10% drop-out rate

Table 3 Sample size and power estimates based on the SCR endpoint

Strain	SCR in aQIV group	SCR in QIV group	Power with Sample size of 2,018 (1,816 evaluable) for NI (SCR margin -10%)
A/H1N1	86%	76%	~100%
A/H3N2	87%	77%	~100%
B (Victoria and Yamagata lineage)	82%	80%	~100%

Statistical Analysis Plan, Protocol Number V118_23
20OCT2022 Final Version 1.0

Thus with 1:1 randomization, assuming that B/Victoria and B/Yamagata are similar, 1,816 evaluable subjects will provide an overall power of 90% to demonstrate the primary objectives of noninferiority and superiority of aQIV vs QIV with one-sided alpha=0.025. Assuming a 10% drop out rate, the total sample size for the study needed is 2,018.

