A nonadjuvanted inactivated quadrivalent influenza vaccine administered as one 0.5 mL intramuscularly into the deltoid muscle. The vaccine is presented in a pre-filled needleless syringe (PFS). Each 0.5 mL dose contains 15 µg HA from each of the four influenza strains recommended by the World Health Organization for the 2021/2022 Northern Hemisphere influenza season for quadrivalent vaccines.		
Statistical Analyses:		
The primary analysis will be conducted on the immunogenicity data collected up to Day 22.		
Sample Size Estimation:		
With 1:1 randomization, a sample size of 1,816 evaluable subjects is chosen so that with one-sided alpha=0.025, there will be at least 90% power to achieve the primary objectives (1a and 1b). Assuming 10% drop out, the total sample size for the study is 2,018 subjects.		

Protocol Number: V118_23

Product Name: aQIV

Document Status: Final Version 3.0, Document Date: 11 Jul 2022

Name of Sponsor:	Protocol number:	Generic name of study vaccine(s):
Seqirus UK Limited	V118_23	MF59-adjuvanted Quadrivalent Subunit Inactivated Influenza Vaccine (aQIV) Licensed comparator: nonadjuvanted Quadrivalent Influenza Vaccine (QIV)

More details on the sample size calculation are provided in Section 8.5, Sample Size and Power Considerations of Primary Objectives.
 
aQIV will be tested against a licensed nonadjuvanted quadrivalent influenza vaccine (QIV). This study is powered to demonstrate the GMT superiority of aQIV vs QIV assessed by the four co-primary endpoints associated with primary objective 1b) at significance level of one-sided $\alpha=0.025$.
 
Hypothesis testing will be carried out by 1a) and 1b) sequentially. Only after the NI objectives are achieved, the superiority objectives will be tested. All tests are carried out with a one-sided alpha of 0.025 for each comparison. No adjustment for multiple endpoints for the primary objectives is necessary.
 
The Per Protocol Set (PPS) will be used for the noninferiority analyses, and the Full Analysis Set (FAS) will be used for superiority analyses.
 
Details on the statistical analysis can be found in Section 8, Statistical Considerations.
		

Interim Analysis: An interim analysis is not planned for this study.
		

Data Monitoring Committee: An independent Data Monitoring Committee will not be utilized for the study.
		

Schema

Table 0-1: Time and Events Schedule

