8.2.1.3 Success Criteria for Primary Immunogenicity Objective(s)

Success criterion for primary immunogenicity objective 1a is defined as:

Noninferiority of the aQIV immune response will be demonstrated if the UL of the 95% CI for the inter-group Day 22 GMT ratio (QIV/aQIV) is ≤ 1.5 for each vaccine strain, and the UL of the 95% CI for the difference in SCR (QIV - aQIV) is $\leq 10\%$ for each vaccine strain.

Success criterion for primary immunogenicity objective 1b is defined as:

Superiority of the aQIV immune response will be demonstrated if the UL of the 95% CI for the inter-group Day 22 GMT ratio (QIV/aQIV) is < 1.0 for at least 2 of the 4 vaccine strains.

The study is considered successful if primary objective 1a is achieved.

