8.5 Sample Size and Power Considerations of Primary Objectives

aQIV will be tested against QIV. The randomization ratio is 1:1 (aQIV:QIV). The study is designed to have at least 90% power to achieve the primary objectives: to demonstrate the noninferiority of GMT and SCR of aQIV vs QIV for all 4 strains, and the superiority (superiority margin of 1) of GMT of aQIV vs QIV for at least 2 of the 4 strains with one-sided significance level $\alpha=0.025$.

The results of a previous clinical study with aTIV and TIV vaccine in subjects 50-64 years of age (Study V7P38) was used to generate assumptions for vaccine effect and sample size.

It is assumed that the differences of $\log_{10}(\text{GMT})$ of A/H1N1 is 0.07, with standard deviation of 0.46 for both treatment arms, 1,816 evaluable subjects will provide at least 90% of power to demonstrate a superiority of aQIV vs QIV for the A/H1N1 strain. The table below shows the power of each comparison based on GMT ratio and SCR data from Study V7P38:

Strain	$\log_{10}(\text{GMT})$ Differences (SD)	Sample Size (Evaluable Subjects) for 90% Power	Power with Sample size of 2,018 for superiority (GMT _r margin of 1) (1,816 Evaluable Subjects)	Power with Sample size of 2,018 for NI (Margin of 0.67)

A/H1N1	0.07 (0.46)	2,018 (1,816 evaluable subjects)	90%	~100%
A/H3N2	0.26 (0.61)	260 (234 evaluable subjects)	~100%	~100%
B	0.14 (0.48)	552 (496 evaluable subjects)	~100%	~100%

Strain	SCR in aQIV group	SCR in Comparator group	Power with Sample size of 2,018 (1,816 evaluable) for NI (margin -10%)
A/H1N1	86%	76%	~100%
A/H3N2	87%	77%	~100%
B	82%	80%	~100%

Abbreviations: aQIV = adjuvanted Quadrivalent Influenza Vaccine; GMT = geometric mean titer; NI = noninferiority; SCR = seroconversion rate; SD = standard deviation.

Thus with 1:1 randomization, 1,816 evaluable subjects will provide an overall power of 90% to demonstrate the primary objectives of noninferiority and superiority of aQIV vs QIV with one-sided alpha=0.025. Assuming a 10% drop out rate, the total sample size for the study needed is 2,018 subjects.

Further details of the sample size calculation will be fully described in the SAP.

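### The concluding overall power of 90% is the A/H1N1 superiority figure; objectives 1a and 1b as defined have at least 99.998% power under the plan's own inputs (minor, conservative)

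*SAP*

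**What the plan says.** SAP section 5 and Protocol 8.5 set out the same calculation. Each opens with a floor, which the SAP words as "The study is designed to have at least 90% power to achieve the primary objectives". Each defines those objectives as noninferiority of GMT and SCR in all four strains plus GMT superiority in at least two. The success criterion for 1b in Protocol 8.2.1.3 likewise asks for superiority "for at least 2 of the 4 vaccine strains".

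The sample size is then derived from one strain. Protocol 8.5 says "1,816 evaluable subjects will provide at least 90% of power to demonstrate a superiority of aQIV vs QIV for the A/H1N1 strain", and SAP section 5 says "at least 90% of power to demonstrate a superiority (GMTr margin of 1) of aQIV vs QIV for the A/H1N1 strain". The tables give about 100% for superiority on A/H3N2 and B, and about 100% for every noninferiority comparison of GMT and SCR.

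Both sections then conclude that "1,816 evaluable subjects will provide an overall power of 90% to demonstrate the primary objectives of noninferiority and superiority of aQIV vs QIV". The SAP attaches a condition to this sentence, "assuming that B/Victoria and B/Yamagata are similar". Protocol 8.5 does not state it.

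The Synopsis gives the floor of at least 90% for 1a and 1b, but also says "This study is powered to demonstrate the GMT superiority of aQIV vs QIV assessed by the four co-primary endpoints" in connection with objective 1b.

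**The concern.** The concluding sentence drops the words that made the opening a floor and presents 90% as the result of the calculation for 1a and 1b together. The only comparison with 90% power in either section is A/H1N1 superiority, and 1b does not require A/H1N1 to succeed: A/H3N2 and one B lineage are enough. On the tables as printed, the power for 1a and 1b cannot be 90%.

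Little is at stake in practice, because the figure errs low. But someone checking the sample size cannot reproduce the stated power for the stated criterion, and might infer that superiority is required in all four strains. The Synopsis reference to four co-primary endpoints encourages that reading.

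**Working it through.** **Inputs** (SAP section 5, Tables 2 and 3; same values in Protocol 8.5)

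- 1,816 evaluable subjects, 1:1, so 908 per arm; one-sided alpha 0.025, z = 1.960.
- log10 GMT difference (SD): A/H1N1 0.07 (0.46); A/H3N2 0.26 (0.61); B 0.14 (0.48), used for both lineages.
- SCR, aQIV vs QIV: A/H1N1 86% vs 76%; A/H3N2 87% vs 77%; B 82% vs 80%.
- 1a: all eight noninferiority tests succeed (GMT ratio margin 1.5, log10 = 0.1761; SCR margin 10 points). 1b: superiority in at least two of four strains.

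**Reproducing the plan's figures**

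For superiority, SE = SD × √(2/908) and power = Φ(difference/SE − 1.960). For A/H1N1, SE = 0.46 × √(2/908) = 0.02159 and 0.07/0.02159 = 3.242. Subtracting 1.960 leaves 1.282, so power = 0.9002 (0.8999 with the noncentral t). 908 is the smallest number per arm that reaches 90% by the normal approximation, and 1,816/0.9 = 2,017.8, rounded up to 2,018. The sizes for the other strains also reproduce: A/H3N2 232 (normal) or 234 (t), B 496.

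**Probability of missing each comparison at 908 per arm**

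For noninferiority, the difference/SE term becomes (difference + margin)/SE. For SCR, SE = √[(p₁(1−p₁) + p₂(1−p₂))/908].

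| Strain | GMT superiority | GMT noninferiority | SCR noninferiority |
|---|---|---|---|
| A/H1N1 | 0.0998 | below 1e-20 | below 1e-18 |
| A/H3N2 | 5.3e-13 | below 1e-20 | below 1e-18 |
| B, each lineage | 1.05e-5 | below 1e-20 | 2.56e-6 |

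The two B entries that matter:

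- Superiority: 0.14/0.02253 = 6.215; 6.215 − 1.960 = 4.255; miss 1.05e-5.
- SCR noninferiority: (0.10 + 0.02)/0.01841 = 6.520; 6.520 − 1.960 = 4.560; miss 2.56e-6.

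**Joint power of 1a and 1b**

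- 1a: the sum of all eight misses is 2 × 2.56e-6 = 5.12e-6, the rest being negligible.
- 1b: if A/H3N2 and one named B lineage both succeed, 1b is met. So P(miss 1b) ≤ 5.3e-13 + 1.05e-5 = 1.05e-5. Under independence it is 1.1e-11.
- Together: P(miss 1a or 1b) ≤ 5.12e-6 + 1.05e-5 = 1.56e-5, so power ≥ 0.99998. This is a sum of miss probabilities, so it holds under any correlation between strains and endpoints.

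**What 90% does correspond to**

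A/H1N1 superiority: 0.9002. Superiority in all four strains, assuming independence: 0.9001. Neither is the two-of-four rule.

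**Size of the gap in subjects**

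With the same inputs, joint power for 1a and 1b first reaches 90% at 278 per arm (556 evaluable) if all endpoints are independent: 1b 0.997 × 1a 0.903 = 0.9004. At 319 per arm (638 evaluable) the sum of misses is 0.0996, so 90% is assured under any correlation. The plan has 1,816. This only measures how far the label is from the criterion; it is not an argument for a smaller trial.

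**The case against.** The strongest reply is that no calculation in the plan is wrong. Every component figure reproduces, the section openings and the Synopsis say at least 90%, and the tables show where 1,816 comes from. On this view the last sentence merely restates the design target. It is true that nobody who reads the whole section will misjudge the basis of the sample size. But the sentence is introduced as a conclusion, omits the qualifier and gives a single value for a named criterion. A true floor elsewhere does not correct it.

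A second reply is that 90% may have been meant as power for superiority in all four strains, which under independence is 90.01%. The documents do not settle which was meant. Neither reading gives the power of 1b as defined.

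Third, inserting *at least* in the two sentences would make them true with less change, and a figure above 99.9% leans on effects from one trivalent study. The shorter edit would indeed cure the falsehood, but the power of the actual criterion would stay unstated. The dependence on assumed effects is met by saying so in the sentence.

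The two side points are clerical. The protocol defers sample size details to the SAP, where the B-lineage condition appears, and the Synopsis phrase refers to objective 1b, whose rule is clear elsewhere. The conclusion does not rest on either.

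**Conclusion.** The concern holds, as a minor point. Under the plan's own inputs the stated overall power is about 10 percentage points below the power of the objectives it names: 90% against at least 99.998%. The 90% is the figure for A/H1N1 superiority. The error is conservative and leaves the adequacy of the sample size, the conduct, the analysis and the control of type I error unaffected.

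The result rests on the effects and SDs taken from Study V7P38, on one B estimate serving both lineages, and on normal approximations. It needs no assumption about correlation.

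**What to change.** Replace the concluding power sentence in both SAP section 5 and Protocol 8.5 with:

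> With 1:1 randomization and one-sided alpha = 0.025, 1,816 evaluable subjects give 90% power for A/H1N1 superiority, the strain that sets the sample size. Power for objectives 1a and 1b as defined (superiority in at least 2 of 4 strains) exceeds 99.9% under the assumed effects, with B/Victoria and B/Yamagata taken as similar.

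This also brings the B-lineage condition into the protocol. In the Synopsis, replace the reference to four co-primary endpoints with the at-least-two-of-four rule of objective 1b. The openings and the Synopsis floor of at least 90% can stay.

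The cost is two sentences and one phrase, with no change to sample size, conduct or analysis.
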